### 1.3 Example Schedule of Activities

	Screening	Baseline				
Day (± Window)	Day -1 or Day 1	Day 1	Daily Until Hospital Discharge (or Daily Until Day 29 While in Hospital)	Day 15 a (±2 days)	Day 29 a (±3 days)	Day 60 a (±4 days) (End of Study)
ELIGIBILITY						
Informed consent	X					
Demographics	X					
Relevant medical history b	X					
Review of SARS-CoV-2 diagnostic tests (obtained during the previous 72 hours, if available)	X					
SARS-CoV-2 diagnostic test c	X					
Inclusion and exclusion criteria	X	X				
12-lead electrocardiogram	X					
STUDY INTERVENTION						
Randomization		X				
Administration of study treatment		Defined in sub-protocol				
Treatment with SoC		SoC will be based on the practices of the study center				
STUDY PROCEDURES						
Physical examination (including height and weight) d	X					
Vital signs, including body temperature, pulse rate, blood pressure, respiratory rate, SpO 2 , FiO 2 e		X f	X	X g	X g	
CCI						
Ordinal scale		X f	X	X	X	X

	Screening	Baseline				
Day (± Window)	Day -1 or Day 1	Day 1	Daily Until Hospital Discharge (or Daily Until Day 29 While in Hospital)	Day 15 a (±2 days)	Day 29 a (±3 days)	Day 60 a (±4 days) (End of Study)
Clinical assessments b		X f	X	X	X	X i
Assessment of floor status (ICU yes/no)		X	X g	X g	X g	
Assessment of rehospitalization for discharged patients j				X	X	X
Concomitant medication review (including use of vasopressors)	X	X f	X	X	X	X
Adverse event evaluation	X	X	X	X	X	X
SAFETY LABORATORY						
Clinical safety laboratory assessments	X k,l	X f,m,n	Days 3 o , 8 m , 22 m , and at discharge m,p All other days while in hospital q	X m,r	X m	
Pregnancy test for females of childbearing potential	X k					
RESEARCH LABORATORY						
CCI						

Abbreviations: ARDS=acute respiratory distress syndrome; eCRF=electronic case report form; FiO2=fraction of inspired oxygen; ICF=informed consent form; ICU=intensive care unit; **CCI**; SARS-CoV-2= severe acute respiratory syndrome coronavirus 2; SoC=standard of care; SpO2=oxygen saturation.

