**Table 3 Clarification of the 8-point Ordinal Scale for Scores 6 Through 8**

Ordinal Scale Score	General Description	Expanded Description
6	Fit-for-discharge but hospitalized	No longer requiring acute in-hospital medical care; clinically stable for discharge, may have ADL limitations, but is awaiting post-hospital/outpatient placement, or may have a delay in sourcing new or additional home care that makes discharge unadvisable.
7	Fit-for-discharge, not hospitalized with limitations in ADLs and/or oxygen needs	Not hospitalized. This category is reserved for patients with limitations in ADL and/or who require home oxygen.
8	Fit-for-discharge, not hospitalized and no limitations in ADL	Not hospitalized. This category describes patients with no limitations in ADL and/or those who have returned to baseline pre-COVID-19 performance.

Abbreviations: ADL = activities of daily living; COVID-19 = coronavirus disease 2019.

The primary endpoint will be time to confirmed clinical recovery through Day 29, ie, fit-for-discharge, as defined by achieving a score of 6, 7, or 8 on the 8-point ordinal scale of clinical severity status, without being rehospitalized through Day 29.

Incidence of patients achieving  $\geq 2$ -point improvement from baseline on the ordinal scale or fit-for-discharge at Day 29, with fit-for-discharge defined as categories 6, 7, and 8 on the 8-point ordinal scale will be a key secondary endpoint.

Distribution across categories on the 8-point ordinal scale at Days 8, 15, and 29, as well as the worst postbaseline score on 8-point ordinal scale from randomization to Day 29, the clinical recovery (based on patients who achieve a score of 6, 7, or 8) on Days 8, 15, and 29, and the sustained clinical recovery as confirmed by Day 60 will be secondary endpoints. ‘Sustained’ is defined as clinical recovery without readmission to a hospital by Day 60.

CCI

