Refer to Section 16.2.2.2 for handling of missing number of ICU days from Day 1 through Day 29.

16.2.1.7. Number of Invasive Mechanical Ventilator Days from Day 1 through Day 29

For each patient, the ‘other secondary efficacy endpoint’ of the number of invasive mechanical ventilator days from Day 1 through Day 29, inclusively, will be considered as an ordinal endpoint and derived similarly to the number of ICU days from Day 1 through Day 29 (refer to Section 16.2.1.6) but using the data collected on the *Supplemental Oxygen and Mechanical Ventilation* page of the eCRF where *Type of supplemental oxygen* is recorded as *Invasive Mechanical Ventilation*.

Refer to Section 16.2.2.2 for handling of missing number of invasive mechanical ventilation days from Day 1 through Day 29.

16.2.1.8. Incidence of Patients with Clinical Recovery by Days 8, 15, and 29

[figure not shown]
An ‘other secondary efficacy endpoint’ is the incidence of patients with clinical recovery at Days 8, 15, and 29, defined as the proportion of patients being fit for discharge (i.e., patients achieving a score of 6, 7, or 8 on the 8-point ordinal scale for clinical severity; refer to Section 16.1.1) at Days 8, 15, and 29, respectively, as per data recorded on the *Ordinal Scale for Clinical Severity* page of the eCRF. It is to be noted that patients with a score of 7 discharged to hospice care will not be considered as being fit for discharge for this ‘other secondary efficacy endpoint’.

Refer to Section 16.2.2.1 for handling of missing clinical recovery status by Days 8, 15, and 29.

16.2.1.9. Incidence of Patients with Sustained Clinical Recovery as Confirmed by Day 60 Follow-up

An ‘other secondary efficacy endpoint’ is the incidence of patients with sustained clinical recovery as confirmed by Day 60 follow-up, defined as the proportion of patients considered as being fit for discharge (i.e., achieving a score of 6, 7, or 8 on the 8-point ordinal scale for clinical severity) through Day 29, without re-hospitalization by Day 60 (refer to Section 16.1.1), as per the *Ordinal Scale for Clinical Severity* and *Hospitalization* pages of the eCRF. It is to be noted that patients with a score of 7 discharged to hospice care before or on Day 29 will not be considered as being fit for discharge for this ‘other secondary efficacy endpoint’.

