Similarly to the primary efficacy endpoint, patients achieving a score of 6 on the ordinal scale for clinical severity before or on Day 29 will be considered as having sustained clinical recovery if they have no worsening of their ordinal scale score by Day 60 (i.e., a score < 6 on the ordinal scale for clinical severity) or were discharged from the hospital after Day 29 and were not re-hospitalized by Day 60.

Refer to Section 16.2.2.1 for handling of missing sustained clinical recovery as confirmed by Day 60 status.

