16.2.2. MISSING DATA IMPUTATION METHOD FOR SECONDARY EFFICACY ENDPOINTS

16.2.2.1. Binary Endpoints

For the *incidence of oxygen-free recovery at Day 29* endpoint, the algorithm defined in Section 16.2.1.1 will first be applied. Then, patients with a missing oxygen-free recovery status at Day 29 will be considered as not having met the event for this key secondary efficacy endpoint.

For the *incidence of patients with ≥ 2-point improvement from baseline or fit for discharge on the ordinal scale at Day 29* endpoint (refer to Section 16.2.1.2), patients with a missing ordinal scale score at Day 29 due to patient’s death, discontinuation from study before or on Day 29 or for any other reason (with the following exception) will be considered as not having met the event at Day 29 for that key secondary endpoint. The only exception is for patients with a missing ordinal scale score at Day 29 for which the latest non-missing ordinal scale score before Day 29 was 7 (but not discharge to hospice care) or 8. These patients will be assumed to be fit for discharge at Day 29 and so, as having met the event.

For the *incidence of all-cause mortality through Day 29* endpoint (refer to Section 16.2.1.3), patients with an unknown alive/death status at Day 29 due to discontinuation from study for a reason other than death or missing data will be considered as alive in the analysis, exception of patients for who the last-missing ordinal scale score was 7 and that have been discharged to hospice care before discontinuing from study before Day 29. These patients will be considered as dead at Day 29 for the main analysis of this key secondary efficacy endpoint.

[figure not shown]
For the *clinical recovery by Day 8* endpoint (refer to Section 16.2.1.8), any patient who died before or on Day 8, discontinued from study before or on Day 8 or with missing clinical recovery status at Day 8 will be considered as not having clinical recovery by Day 8. Missing *clinical recovery by Days 15 and 29* will be handled similarly.

For the *sustained clinical recovery as confirmed by Day 60* follow-up endpoint (refer to Section 16.2.1.9), any patient who died before or on Day 60, discontinued study before Day 60 or with a missing 8-point ordinal scale score at Day 60 will be counted as not having sustained clinical recovery.

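### Sustained recovery: a discharged patient documented as alive and not readmitted at Day 60 is scored as a failure if the Day 60 ordinal score is missing

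*SAP*

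**What the plan says.** Protocol 8.1.1 says that sustained recovery "is defined as clinical recovery without readmission to a hospital by Day 60". Master SAP 16.2.1.9 makes this operational as a score of 6, 7 or 8 "through Day 29, without re-hospitalization by Day 60", read from the ordinal scale and hospitalization pages of the eCRF. Patients discharged to hospice by Day 29 are excluded.

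Later ordinal scores enter by one route only. A patient who reached a score of 6 by Day 29 qualifies "if they have no worsening of their ordinal scale score by Day 60", or alternatively if they "were discharged from the hospital after Day 29 and were not re-hospitalized by Day 60".

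The missing-data rule in Master SAP 16.2.2.1 fails "any patient who died before or on Day 60, discontinued study before Day 60", and also any patient "with a missing 8-point ordinal scale score at Day 60 will be counted as not having sustained clinical recovery". It makes no exception for discharged patients.

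The Schedule of Activities (Protocol 1.3) lists the ordinal scale and "Assessment of rehospitalization for discharged patients" as separate rows, both due at Day 60. The readmission item is recorded as yes or no, with dates.

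**The concern.** The definition and the missing-data rule are keyed to different variables. For a discharged patient the definition needs readmission status; the rule tests whether a score exists. A patient reached at Day 60, recorded as alive and not readmitted, but with the ordinal scale left blank, has a known outcome. The rule scores that patient as a failure, so it overrides a known success instead of being cautious about an unknown outcome.

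At stake is the accuracy of the reported incidence in each arm and, depending on how the blanks fall, of the comparison. Master SAP 16.2.4 plans no sensitivity analysis for the non-key secondary endpoints, so nothing in the plan would reveal the effect.

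**Working it through.** **1. Does the Day 60 score carry information for a discharged patient?**

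- On the 8-point scale, 1 is death, 2 to 6 are in hospital, and 7 and 8 are out of hospital.
- A living patient who is not in hospital can therefore only score 7 or 8. Both are in the recovery range.
- Once alive and not readmitted are documented, the missing score could not have turned success into failure. Hospice discharge is read from the hospitalization page, not from the Day 60 score.
- For a patient never discharged, who qualifies by staying at 6, the later scores do decide the outcome. There a missing score is a real gap.

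**2. How does the SAP treat the same gap elsewhere?**

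- 16.2.1.9 points to 16.2.2.1 for a missing sustained-recovery *status*; 16.2.2.1 answers with a missing *score*.
- Oxygen-free recovery: the algorithm is applied first, and only a missing status is failed.
- Clinical recovery by Days 8, 15 and 29: a missing status is failed.
- Improvement or fit for discharge at Day 29: a missing score after a last score of 7 (not hospice) or 8 is counted as success.
- Primary endpoint (16.1.1): a score of 7 (not hospice) or 8 with no re-hospitalization is an event, with no requirement for a score on Day 29 itself.

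**3. Size**

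The documents give no rate, power or missingness for sustained recovery, so there is no figure of its own to reproduce. For scale only, I borrow the planning rates of the second key secondary endpoint (Master SAP 7.1): 70% control, a 9.2-point increase to 79.2%, 350 per arm, two-sided 0.05.

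Power = Φ{[√n·d − 1.96·√(2p̄(1−p̄))] / √(p1(1−p1) + p2(1−p2))}, with n = 350, d = 0.092 and p̄ = 0.746:

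(1.7212 − 1.96 × 0.6156) / 0.6122 = 0.841, so power is 80.0%, matching the approximately 80% stated for that endpoint.

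Let m be the share of *true successes* known to be alive and not readmitted but without a Day 60 score. Reported rate = true rate × (1 − m). The values of m are assumptions.

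| m control / active | Control | Active | Difference (points) | Relative risk | Odds ratio | Power |
|---|---|---|---|---|---|---|
| 0 / 0 | 70.0% | 79.2% | 9.2 | 1.13 | 1.63 | 80% |
| 2% / 2% | 68.6% | 77.6% | 9.0 | 1.13 | 1.59 | 77% |
| 5% / 5% | 66.5% | 75.2% | 8.7 | 1.13 | 1.53 | 72% |
| 10% / 10% | 63.0% | 71.3% | 8.3 | 1.13 | 1.46 | 65% |
| 20% / 20% | 56.0% | 63.4% | 7.4 | 1.13 | 1.36 | 51% |
| 5% / 10% | 66.5% | 71.3% | 4.8 | 1.07 | 1.25 | 28% |
| 10% / 5% | 63.0% | 75.2% | 12.2 | 1.19 | 1.78 | 94% |

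Example at 5% / 5%: 0.70 × 0.95 = 0.665 and 0.792 × 0.95 = 0.7524; difference 0.0874; relative risk 0.7524 / 0.665 = 1.13; odds ratio (0.7524/0.2476) / (0.665/0.335) = 1.53. Patients misclassified: 350 × 0.70 × 0.05 = 12.2 and 350 × 0.792 × 0.05 = 13.9.

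The level falls in every row with m above zero. The difference falls when m is equal, and can move either way when it is not.

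**The case against.** The strongest defence is that the endpoint is recovery confirmed at the Day 60 follow-up, and that a Day 60 score shows the follow-up took place. In the primary algorithm (Master SAP 16.1.1), re-hospitalization is detected by the presence of a later hospitalization record. On that method an absent record looks the same whether the patient was not readmitted or was never reached. The SAP does not say that the yes/no readmission answer is used. For patients without a documented answer the rule is ordinary failure imputation, in line with most of the other binary rules. This part stands, and those patients should stay failures.

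The group at issue may also be very small or empty. The score and the readmission item fall due at the same contact, by telemedicine for discharged patients. Choosing between 7 and 8 depends on activity limits and home oxygen, which can be asked by telephone. The footnote to the Schedule of Activities allows for assessments missed by telephone, but its example is vital signs. This limits the size of the problem; it does not make the rule right for a patient whose outcome is documented.

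A reader might infer that the rule costs the better arm more and so dilutes the treatment effect. The documents do not support that as a general statement. It needs similar m in both arms, which nothing establishes. Even then only the risk difference and the odds ratio move; the relative risk, also reported under Master SAP 16.2.3.1, does not.

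**Conclusion.** The rule as written conflicts with the endpoint definition for one group: discharged patients documented at Day 60 as alive and not readmitted, with no ordinal score. Each such patient is a known success scored as a failure, and incidence in that arm is understated by the factor (1 − m).

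A reader might go further and infer that a material number of patients is misclassified, or that every missing Day 60 score is wrongly handled. Neither is supported. The documents give no m; the percentages above rest on assumed m and on rates borrowed from another endpoint. Patients whose readmission status is also missing are correctly treated as unconfirmed. The direction of any bias in the comparison depends on m by arm.

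The consequence is limited. This is an other secondary endpoint outside the testing hierarchy, with nominal p-values only (Master SAP 7.4). The COV-01-004 SAP takes the Master SAP efficacy analyses as they stand. The COV-01-001 and COV-01-005 SAPs inherit the missing-data rule but report only descriptive incidence with confidence intervals. It is a minor correction, worth making because it is cheap.

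**What to change.** Replace the sentence on sustained recovery in Master SAP 16.2.2.1 with, for example:

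*Patients who died by Day 60, who discontinued before Day 60, or whose vital status or readmission status through the Day 60 visit is unknown, are counted as failures for sustained recovery. A missing Day 60 ordinal score is counted as failure only for patients never discharged from the hospital.*

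State alongside it that readmission status is known only when the yes/no item has been answered at the Day 60 visit, so that an absent hospitalization record is not read as no readmission. This keeps the requirement for a confirmed Day 60 follow-up.

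The cost is a sentence or two in the Master SAP and a small programming change. No new data are needed, and the sub-protocol SAPs take up the change by reference. Reporting how many patients change classification between the two rules, by arm, would show whether the point mattered.

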16.2.2.2. Ordinal Endpoints

Missing *ordinal scale scores* will be imputed as follows for the distribution of patients across the categories of the 8-point ordinal scale for clinical severity at Day 8 endpoints (refer to Section 16.2.1.4):

CCI			
PPD		Version Number:	Amendment 1, v1.0
		Version Date:	23Apr2021
CCI			

- Patients who died prior to Day 8 will have a score of 1 used for Day 8;
- For all other occurrences of patient with missing ordinal score at Day 8 (e.g., patients who discontinued from the study before Day 8, etc.), the last non-missing post-baseline ordinal scale score before Day 8 (included data collected at unscheduled post-baseline visits) will be used to impute the missing ordinal scale score at Day 8 exception of patients for who the last non-missing post-baseline ordinal scale score before Day 8 is 7 that were discharged to hospice care. For these patients, the missing ordinal scale score at Day 8 will be imputed to 1.

Missing ordinal scale score at Days 15 and 29 will be imputed similarly.

For the *worst post-baseline score on the 8-point ordinal scale from baseline to Day 29* endpoint (refer to Section 16.2.1.5), patients who have died prior to Day 29 will have their worst post-baseline ordinal scale score from Day 1 to Day 29 set to a score of 1. For patients who are alive at Day 29, no imputation of missing post-baseline ordinal scale scores will be performed. The worst post-baseline ordinal scale score will be identifying among the non-missing post-baseline ordinal scale scores (including data collected at unscheduled post-baseline visits).

For the *number of ICU days and number of invasive mechanical ventilation days* endpoints (refer to Sections 16.2.1.6 and 16.2.1.7, respectively), missing data will not be imputed.

[figure not shown]

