scale score, while patients with a score of 7 discharged to hospice care will be considered as not having met the event, also regardless of their change from baseline in ordinal scale score. For patients hospitalized and not considered as fit for discharge at Day 29 i.e., patients with an ordinal scale score < 6, the ‘≥ 2-point improvement from baseline’ requirement (yes or no) will be established based on the patient’s change from baseline in the ordinal scale at Day 29, where change from baseline will be computed as defined in Section 6.5.

Refer to Section 16.2.2.1 for handling of missing ≥ 2-point improvement from baseline or fit for discharge on the 8-point ordinal scale for clinical severity status.

16.2.1.3. Incidence of All-Cause Mortality through Day 29

The third key secondary efficacy endpoint is the incidence of all-cause mortality through Day 29, defined as the proportion of patients having died due to any cause before or on Day 29. Patients’ alive/death status by Day 29 will be determined based on data captured on the *Death Details* page of the eCRF. If a patient does not have any data captured on the *Death Details* page of the eCRF by Day 29 but his/her ‘subject status’ captured on the *Contact* page of the eCRF at Day 29 is alive or he/she had some data captured on any other page of the eCRF on or after Day 29, he/she will be considered alive on Day 29.

Refer to Section 16.2.2.1 for handling of missing alive/death through Day 29 status.

[figure not shown]
16.2.1.4. Distribution of Patients across the Categories of the 8-point Ordinal Scale for Clinical Severity at Days 8, 15, and 29

An ‘other secondary efficacy endpoint’ is the distribution of patients across the categories of the 8-point ordinal scale for clinical severity at Days 8, 15, and 29 i.e., the proportion of patients in each category of the 8-point ordinal scale for clinical severity at Days 8, 15, and 29. It is to be noted that patients with a score of 7 discharged to hospice care will be pooled with patients with a score of 1 (death) for this ‘other secondary efficacy endpoint’.

Refer to Section 16.1.1 for the description of the 8-point ordinal scale and to Section 16.2.2.1 for handling of missing ordinal scale scores.

16.2.1.5. Worst Post-Baseline Score on 8-point Ordinal Scale from Baseline to Day 29

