An ‘other secondary efficacy endpoint’ is the worst post-baseline score (lower scores are worse) through Day 29 in the 8-point ordinal scale (refer to Section 16.1.1), derived from all scores recorded after baseline up to and including Day 29. It is to be noted that patients with a score of 7 discharged to hospice care will be considered as having a

score of 1 (death) instead of a score of 7 for this ‘other secondary efficacy endpoint.

Refer to Section 16.2.2.2 for handling of missing ordinal scale scores.

16.2.1.6. Number of ICU Days from Day 1 through Day 29

An ‘other secondary efficacy endpoint’ is the number of ICU days from Day 1 through Day 29. This endpoint will be considered as an ordinal endpoint.

For each patient, the number of ICU days from Day 1 through Day 29 will be derived based on the sum of the duration of any episodes of ICU admission between Day 1 and Day 29, inclusively, for patients who were alive on Day 29. Episodes of ICU admission will be identified based on data recorded on the *Hospitalization* page of the eCRF, where *Hospitalization Status* is recorded as *ICU/HDU*. For patients who were discharged to hospice care or died before or on Day 29, the number of ICU days from Day 1 through Day 29 will be set to 30 (worst possible scenario).

The duration, in days, of an episode of ICU admission will be derived as follows:

- Duration of an episode of ICU admission (days) = (Date of ICU discharge – Date of ICU admission) + 1

[figure not shown]
If the start date of an episode of ICU admission is prior to Day 1, it will be set to the date of Study Day 1 (refer to Section 6.1) when deriving ICU duration for that episode.

If an episode of ICU admission is ongoing at Day 29 or at the time of analysis, the stop date of the admission will be set to the minimum of:

- The start date of any subsequent ICU admission;
- Day 29;
- The data cut-off date for the analysis.

If there are any overlapping dates of ICU admission, a Day will only be counted once when deriving the overall number of ICU days for a patient. For example, if a patient has a record where the start and stop Study Days of the ICU/HDU admission are Day 3 and Day 10, respectively, and another record where the start and stop Study Days of ICU/HDU admission are Day 9 and Day 12, respectively, Days 9 and 10 will be counted only once in the overall number of ICU days for that patient.

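### Master SAP 16.2.2.2: a death on Day 8, 15 or 29 with no score that day is carried forward as a living score, and a Day 29 death has no defined worst score unless a 1 was recorded

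*SAP*

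**What the plan says.** Master SAP 16.2.2.2 has two rules for deaths on the ordinal scale.

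- **Distribution at Days 8, 15 and 29.** The section sets out how missing scores are filled. For Day 8: "Patients who died prior to Day 8 will have a score of 1 used for Day 8". The next rule begins "For all other occurrences of patient with missing ordinal score at Day 8" and uses "the last non-missing post-baseline ordinal scale score before Day 8". The exception is a patient whose last score was a 7 with discharge to hospice, for whom "the missing ordinal scale score at Day 8 will be imputed to 1". Then: "Missing ordinal scale score at Days 15 and 29 will be imputed similarly".
- **Worst post-baseline score through Day 29.** The branch for deaths assigns a 1. It reads, in part: "patients who have died prior to Day 29 will have their worst post-baseline ordinal scale score from Day 1 to Day 29 set to a". A second branch covers patients alive at Day 29, for whom nothing is imputed and the worst recorded score stands.

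Other sections of the same SAP include the day itself. Mortality (16.2.1.3) is "defined as the proportion of patients having died due to any cause before or on Day 29". ICU days (16.2.1.6) are set to 30 "For patients who were discharged to hospice care or died before or on Day 29", and ventilator days (16.2.1.7) are derived in the same way. In 16.2.2.1, a patient who dies up to and including Day 8 has not recovered by Day 8, and Days 15 and 29 are handled alike. The primary endpoint algorithm (16.1.1) and oxygen-free recovery (16.2.1.1) also count a Day 29 death as a death by Day 29.

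**The concern.** The two rules in 16.2.2.2 stop one day short of the rules around them, and no reason is given. A patient who dies on a target day can therefore be dead in one table and alive in another from the same analysis. The ordinal scale has death as its worst category, so a missed death moves a patient away from the extreme that these tables exist to show. The order can also be odd: a living patient discharged to hospice with a 7 is treated as a 1, while a patient who died on the target day may stay at 2 or higher. For the worst score, the programmer has to guess.

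The affected outputs are the ordinal distributions, the worst score, and the proportional-odds models and shift tables of 16.2.3.2.

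**Working it through.** No figure in the plan is at issue, so the check is a comparison of rules, then traced records, then a size.

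**1. How each rule treats a death on the target day**

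- Distribution, Days 8, 15 and 29 (16.2.2.2): outside the death rule. If the score is missing, it is carried forward.
- Worst score through Day 29 (16.2.2.2): a Day 29 death is neither before Day 29 nor alive at Day 29. No branch applies.
- Mortality through Day 29 (16.2.1.3): counted as a death.
- ICU and ventilator days through Day 29 (16.2.1.6, 16.2.1.7): set to 30.
- Clinical recovery by Days 8, 15 and 29 (16.2.2.1): not recovered.

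**2. Traced records**

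- (a) Score 2 on Day 28, death on Day 29, no Day 29 score. Mortality: yes. ICU days: 30. Recovery at Day 29: no. Distribution at Day 29: 2. Worst score: undefined by the rule; taking recorded scores alone would leave a living score.
- (b) As (a), but death on Day 28. Distribution at Day 29: 1. Worst score: 1.
- (c) Discharged home (not hospice) with a 7 on Day 5, death on Day 8. The Schedule of Activities (Protocol 1.3) has the scale daily until discharge and then at Days 15, 29 and 60, so no Day 8 score is scheduled. Distribution at Day 8: 7. Recovery by Day 8: no. At Days 15 and 29 the patient is correctly a 1.
- (d) Death on Day 29 and the site enters a 1 that day. Distribution: 1. Worst score: 1, because 16.2.1.5 uses all scores recorded through Day 29. There is no gap.

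Records (a) and (c) show the fault, (b) shows that it turns on a single day, and (d) shows when it does not arise.

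**3. Size**

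Inputs from SAP 7.1: 350 patients per arm; Day 29 mortality 15% on control and 8.25% under the planning alternative. Assumption, not in the documents: deaths are spread evenly over 29 days.

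Deaths per arm on one target day = 350 × mortality / 29.

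- At 15%: 350 × 0.15 / 29 = 52.5 / 29 = 1.8. At half to double that daily rate: 0.9 to 3.6.
- At 8.25%: 350 × 0.0825 / 29 = 28.875 / 29 = 1.0. At half to double: 0.5 to 2.0.

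Only the deaths with no 1 recorded that day are affected, so for a given daily rate each figure is a ceiling. Each target day has its own set of patients, since a Day 8 death is already a 1 at Days 15 and 29.

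The two sub-protocols stopped early are smaller. COV-01-001 expects about 34 patients (its SAP, section 16): 34 × 0.15 / 29 = 0.2 deaths on a given day over both arms. COV-01-005 expects fewer than a third of about 700 (its SAP, section 16): 233 × 0.15 / 29 = 1.2 at most. Both inherit the imputation rule from the Master SAP, but neither does efficacy inference.

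**The case against.** The best defence is that the rule for the distribution fills missing scores only. Category 1 of the scale is death, and the scale is scored daily in hospital. A death on the target day can be entered as an observed 1, after which no scores exist, so imputation would be needed only for later days. On that view, stopping at the day before is coherent.

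This stands as a limit on the point, but it does not close the gap. Nothing in the documents requires a 1 to be entered on the day of death. The SAP takes death status from the Death Details page, not the ordinal scale page. A discharged patient has no Day 8 score scheduled at all. SAP 6.4 does map discharge and early termination data to a scheduled visit with missing data, but it does not say that a death produces a score.

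Several stronger readings are tempting, and the documents do not support them:

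- *Every patient who dies on a target day is scored as living.* A recorded 1 stands.
- *Death before the day is the only route to a 1.* Hospice discharges with a 7 are a second route.
- *The worst score of a Day 29 death is expressly a living score.* It is left undefined.
- *The clash with mortality exists at all three days.* Mortality and ICU or ventilator days run to Day 29 only. At Days 8 and 15 the clash is with clinical recovery.
- *Section 16.2.2.1 shows that Day 29 deaths lack a score, because it mentions Day 29 scores missing through death.* Any earlier death produces the same missing score.

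**Conclusion.** The point holds as a gap in wording with a small effect. A patient who dies on Day 8, 15 or 29 with no score that day receives a living score in the distribution. A Day 29 death has no defined worst score unless a 1 was recorded. Both differ from the SAP's own treatment of the same death in the mortality, ICU and ventilator-day tables (Day 29) and the recovery table (all three days).

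The size is at most about 1.8 patients per 350 per target day at 15% mortality, or about 1.0 at 8.25%. It rests on an even spread of deaths and on the unknown share of deaths for which sites enter a 1. In record (a) the error is one category; in record (c) it runs from 7 to 1. Nothing in the documents suggests that it would differ by arm.

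A reader might infer that the trial's efficacy conclusions are at risk. They are not: SAP 7.4 and 16.2.3 give only nominal p-values for these other secondary endpoints, and the primary and key secondary endpoints use the inclusive wording wherever they refer to death by Day 29. The proportional-odds models remain in force only for COV-01-004, because COV-01-001 and COV-01-005 report counts and percentages.

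**What to change.** In both rules of Master SAP 16.2.2.2, change the death condition from *prior to* to *before or on* Day 8, 15 or 29 as applicable, and take the date of death from the Death Details page. The worst-score rule then has two complete branches, and the ordinal tables agree with the mortality and recovery tables.

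One further clause is worth a decision. A living score entered earlier on the day of death is not missing, so the distribution rule would not reach it. The SAP should say whether the date of death takes precedence there. Full agreement with the recovery table needs it to, but that means setting aside an observed score, so it is a choice to state and not an error to correct.

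The cost is a wording change and the matching line of programming. The COV-01-001 and COV-01-005 SAPs pick it up by reference. No data collection, sample size or error control is touched.
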